5. STUDY OBJECTIVES OR HYPOTHESES

5.1 Hypothesis

We hypothesize that idebenone, through its combined effect on facilitation of mitochondrial metabolism and limitation of oxygen radical-induced CNS damage, will inhibit CNS tissue destruction in PP-MS patients.

5.2 Goals of the study

The primary goals are:

1. To extend long-term (36 months) data on the safety and tolerability of idebenone at 2250 mg/day in patients with PP-MS.
2. To extend CSF biomarker data by significantly expanding (up to 2 fold if all eligible patients proceed to IPPOMS-E) the matched “baseline” vs. “idebenone treatment” CSF samples, which will be analyzed for biomarkers of oxidative stress, mitochondrial function and CNS tissue integrity.
3. To extend efficacy data for idebenone on CNS tissue destruction as measured by quantitative imaging biomarkers and clinical/functional biomarkers in patients previously completing IPPoMS (Protocol Number 09-N-0197). For patients originally randomized to active drug, the idebenone longitudinal data will be extended for total of 3 years, for patients originally randomized to placebo, 3 year pre-treatment or placebo-treatment period will be compared to 1 year idebenone therapy period.

The secondary goals are:

1. To further investigate the mechanism of action of idebenone in PP-MS.
2. To better define biomarkers indicative of therapeutic effect of idebenone on mitochondrial dysfunction and on limiting oxidative damage in PP-MS patients.

6. SUBJECTS

6.1. Study population

Eligible patients completing the IPPoMS trial will be offered the opportunity to enroll in this IPPoMS-E study.

It is important that no break in study medication between the IPPoMS randomized phase and the present study occurs. Such a break in therapy will render interpretation of study outcomes in this trial more difficult. However, if a patient does finish the IPPoMS randomization phase before this IPPoMS-E study is approved for use, they will be allowed to enter the IPPoMS-E trial.

6.2. Inclusion criteria

1. Completion of 3 years in study IPPoMS (Protocol Number 09-N-0197)
2. Able to provide informed consent
3. Adults, at least 18 years of age.
4. Willing to participate in all aspects of trial design and follow-up

5. If able to become pregnant or to father a child, agreeing to commit to the use of a reliable/accepted method of birth control (i.e. hormonal contraception (birth control pills, injected hormones, vaginal ring), intrauterine device, barrier methods with spermicide (diaphragm with spermicide, condom with spermicide) or surgical sterilization (hysterectomy, tubal ligation, or vasectomy)) for the duration of treatment arm of the study

6.3. Exclusion criteria

1. Pregnant or lactating women. All women of child-bearing potential must have a negative pregnancy test
2. Patients dropping out of IPPoMS due to AEs considered related to study medication

7. STUDY DESIGN AND METHODS

7.1 Study overview

This is a Phase II open-label trial of the safety and efficacy of idebenone at 2250 mg/day with one year treatment period. Patient-specific biomarkers of disease progression and longitudinal neuroimaging and clinical data will be collected as for the randomized study.

7.2 Recruitment

Eligible patients completing the IPPoMS (Protocol Number 09-N-0197) will be offered the opportunity to enroll in this open-label extension study IPPoMS-E.

7.3 Screening methods

Not applicable.

7.4 Study design

Patients will be given idebenone (2250 mg/day, given as five 150 mg tablets, three times a day) and will be followed by combined neurological, neuroimaging and research biomarker/immunological evaluations every 6 months for 1 year. In addition, patients will have safety labs drawn at month 25 which can be drawn at NIH or at an outside lab with results (including normal values) communicated to NIH investigators. Telephone interviews will occur 1 week, 1 month (Mo 25) and 2 months (Mo 26) after initiation of dosing. Patient's safety and change in neurological function will be assessed during the telephone interview with an investigator (Figure 2).

The IPPoMS-E Baseline information will be provided by the results of the IPPoMS Month 24 assessments.

The time commitment will include extension of the last visit on IPPoMS trial (which will serve as initial visit in IPPoMS-E trial) and 2 additional prolonged outpatient or inpatient visits in the 1 year

period. Each prolonged visit will have procedures that together last at least 8 hours spread over 1-3 days.

According to negotiated MCRADA, Santhera Inc. will supply sufficient amount of idebenone for completion of the proposed trial (i.e. 1 year dosing for up to 85 patients). There is no negotiated provision for Santhera to continue to provide drug on a compassionate basis for any of the patients after completion of the trial.

7.5 Study procedures

7.5.1 Study visits

The last study visit in IPPoMS will serve as the baseline visit for this extension study, at which time informed consent will be obtained and patient will undergo the first lumbar puncture and associated research bloodwork under IPPoMS-E protocol. Each subsequent IPPoMS-E study visit (Figure 2) and MRI should occur as indicated. These time points are approximated. To accommodate for patient scheduling needs or clinical necessity, study visits will be accepted within a +/- 4 week window of the time points noted. Biological samples (CSF, whole blood or apheresis sample) should be collected within 4 weeks of the MRI examination as indicated in Figure 2. Blood samples at the IPPoMS mo 24 visit and 36 month IPPoMS-E will be collected concomitantly with CSF samples in the IPPoMS-E trial.

Because most patients enrolled in IPPoMS trial do not live locally, their clinical visits will be associated with travel to NIH for either inpatient or outpatient visits lasting 1-3 days. During these extended visits all study procedures pertaining to a specific study time point will be performed. We estimate that the total duration of all study procedures pertaining to a single study timepoint is 8-12 hours.

7.5.2 Clinical and functional evaluations:

1. Comprehensive neurological evaluation
2. Expanded Disability Status Scale (EDSS (*Kurtzke 1983*))
3. Scripps Neurological Rating Scale (NRS (*Sharrack and Hughes 1996*))
4. MS Functional Composite Scale (MSFC (*Cutter, Baier et al. 1999*), which consists of 3 functional tests:
 - a. Paced Auditory Single Digit Addition Test (PASAT) – measure of cognitive skills
 - b. Timed 25 foot walk – measure of ambulation
 - c. 9-hole peg test – measure of fine finger motor movements
5. Symbol Digit Modality Test (*Sepulcre, Vanotti et al. 2006*)
6. Extensive evaluation of strength, balance and gait within the context of a physical therapy (PT) evaluation will be performed if the subject is not too disabled to participate in these evaluations safely and reliably. This optional evaluation will be conducted in the Biomechanics Laboratory of the Rehabilitation Medicine Department, NIH, CC. It will include, but may not be limited to, the following:
 - a. Evaluation of strength and tone
 - b. Evaluation of gait

c. Balance assessment

7.5.3 Neuroimaging evaluation:

MRI imaging will consist of:

- 1) MRI of the brain, which will be performed every 6 months. This MRI will focus on quantitative and volumetric analyses of brain structure and tissue integrity. Inflammatory activity is less prominent in PP-MS as compared to RR-MS and consequently, the vast majority of PP-MS patients do not have evidence of gross blood-brain barrier (BBB) disruption as measured by contrast-enhancing lesions (CEL). Therefore, gadolinium (Gd) may not be administered during every scan. Clinical judgment will determine if Gd is administered during the remaining 3T brain MRI scans. The total scan time without Gd administration is approximately 90 minutes. With Gd, the scan time increases to 2 hours.
- 2) MRI of the spinal cord. This will focus on analysis of spinal cord volume and detection of lesions. We will investigate the feasibility and value of quantitative spinal cord structural integrity measures as well. This scan will be performed at Mo 30 and Gd administration will be based on clinical judgment. The total scan time is approximately 75 minutes without Gd and 90 minutes with Gd.

7.5.4 Optical coherence tomography (OCT)

OCT will be performed at the conclusion of IPPoMS-E trial. OCT is a new noninvasive high-resolution method that measures the retinal nerve fiber layer (RNFL) thickness. It works by measuring the echo time delay and intensity of back-reflection of light from different structures in the eye. Recent studies have shown that OCT can detect RNFL thinning, possibly due to axon degeneration, within the retinas of patients with MS, regardless of a clinical history of optic neuritis (*Kallenbach and Frederiksen 2007*). Moreover, RNFL thickness appears associated with global brain atrophy, (manifested by increasing CSF volume) (Gordon-Lipkin, Chodkowski et al. 2007). As discussed, reliable methods of measurement of neurodegeneration in MS are lacking. While a more thorough characterization is needed, evidence to date suggests that OCT may be developed as a novel measure of neuronal/axonal destruction reflective of neurodegeneration in MS with both diagnostic and prognostic potential (*Gordon-Lipkin, Chodkowski et al. 2007; Kallenbach and Frederiksen 2007*).

7.5.5 Transcranial magnetic stimulation (TMS) and Central motor conduction time (CMCT) calculation

TMS and CMCT may be performed for clinical care.

Neurophysiological testing, can assess the intactness of conduction through the long tracts, such as the corticospinal tract (CST) (*Ravnborg 1996*). Because CST is invariably affected in PP-MS, the use of motor evoked potentials (MEP) may be performed for clinical care. TMS is a non-invasive technique for evaluating the function of central motor pathways. Single pulse TMS is used to determine the motor evoked potential (MEP), the response generated by excitation of cortical neurons and recorded at the target muscle, and is used to calculate the central motor conduction time

(CMCT). In MS patients, CNS dysfunction manifests itself in the form of slowed conduction through demyelinated portions of the corticospinal tracts or more severe disruption of conduction as a result of axonal loss or severe demyelination. This results in a prolongation of CMCT or dispersion of the MEP response such as in a conduction block with resultant decrease in MEP amplitude (*Hess, Mills et al. 1987; Schriefer, Hess et al. 1989*). In progressive MS patients, CMCT has been shown to correlate with the presence of new spinal cord lesions on MRI and changes in the leg CMCT (*Kidd, Thompson et al. 1998*). There is other evidence that suggests that progressive MS patients have greater prolongation of the CMCT compared to relapsing-remitting MS, irrespective of MRI lesion load, suggesting that progressive MS has more perturbations of the corticospinal tracts than are radiologically discernible (*Humm, Z'Graggen et al. 2004*).

7.5.6 Immunological and laboratory evaluation:

The immunological and laboratory evaluation will include:

1. Clinical blood-work (clinical care/safety): CBC, Chemistry panel including liver function tests will be performed one month after initiation of open label dosing (Mo 25), Mo 30, and Mo 36. Laboratory evaluations that are performed at times when no NIH MRI/clinical visit is scheduled (Mo 25) can be performed outside of NIH with results (including normal values) communicated to NIH investigators. PT/PTT and PFA panel may be collected as additional safety measures at month 30 and 36. Urine analysis (UA) will be performed every 6 months. Pregnancy tests (for females of child-bearing potential) will be collected up to 24h preceding every MRI exam. All safety laboratory evaluations are represented in the clinical trial scheme on Figure 2.
2. Research Blood (up to 40 cc total): Research blood will be obtained concomitantly with the LP Lumbar puncture (research): Every patient will undergo a lumbar puncture at the beginning of IPPoMS-E trial (month 24) and after 1 year of therapy (month 36). This procedure is performed solely for research purposes. From 15-20cc of research specimen, immune cells will be isolated and expanded and the CSF supernatant will be aliquoted and stored. In certain cases (generally with participants who are obese, who have limited mobility, or who have lumbar spondylosis), the procedure may be performed under fluoroscopic guidance by a credentialed neuroradiologist in Diagnostic Radiology. This involves a small amount of ionizing radiation (0.023 rem per year). This is substantially less than the limits imposed by the guidelines of the NIH Radiation Safety Committee (5.0 rem per year for adults).
3. Lumbar puncture procedure last from 30 minutes to 2 hours.
4. Pharmacokinetic (PK) studies (research): Random sampling PK studies may be performed from the CSF at the time of LP, for the analysis of IDE and IDE+IDE-C and the metabolites QS-10, QS-6 and QS-4, as well as QS10+QS10-C, QS6+QS6-C and QS4+QS4-C. Samples will be put on ice immediately and centrifuged at 4°C at 1500 g for 10 minutes within 30 minutes after sampling. The cell-free aliquots will be separated and stored separately in polypropylene tubes with a minimum of 0.5ml of CSF per tube. Samples will be stored between -70 and -80°C. The CSF will be collected for possible future PK studies to be performed by Santhera Pharmaceuticals upon completion of the collection of all trial samples, using a validated LC-MS/MS method (Inovalab, Reinach, Switzerland)
5. Lymphocytapheresis (research): collecting between $2-4 \times 10^9$ peripheral blood mononuclear cells PBMC, will be performed after 1 year of idebenone therapy (Mo 36). This procedure is performed solely for research purposes. This procedure may last up to 2.5 hours. If the

participant is unable to undergo lymphocytapheresis for any reason, 120 cc of whole blood in a heparinized syringe will be collected in its place. The collected mononuclear cells will be used for immunological studies.

7.5.7 Drug administration:

A copy of this protocol has been submitted to the FDA under the existing IND for review. Santhera provided a letter of cross-reference to the IND held by them.

Idebenone (150mg tablets) will be administered orally as five tablets, three times per day with food. Patients will receive a 6 month supply of the study medication. Patients will record drug administration in a drug diary. Remaining pills and bottles will be counted during clinic visits every 6 months to assess overall drug compliance.

Idebenone is a short-chain benzoquinone derivative of similar structure to ubiquinone (coenzyme Q₁₀). This compound was synthesized and developed initially by Takeda Chemical Industries, Ltd. (Osaka, Japan) and designated as CV-2619. The chemical name for idebenone is 6-(10-Hydroxydecyl)-2,3-dimethoxy-5-methyl-1, 4-benzoquinone. Santhera Pharmaceuticals (Switzerland) Ltd, will supply the drug for this study as specified by a clinical trial agreement. Idebenone is formulated as film-coated 150 mg tablets. For list of inactive ingredients see section 4.5.4.

Idebenone with a certificate documenting analytical results, release of the product for the clinical study and shelf life will be provided to the NINDS by Santhera Pharmaceuticals (Switzerland) Ltd. Idebenone tablets are supplied in high density polyethylene (HDPE) bottles, should be stored at room temperature (15-25°C) and must be protected from direct sunlight. Temperature excursions are permitted as follows: up to 30°C for 12 months, up to 40°C for 6 months.

7.5.8 Records:

The NINDS/Clinical center record will be used for trial-related documentation. Specific trial-related pages will include:

Inclusion and exclusion criteria checklist

Documentation of the history and physical examination (using structured NIB progress note)

1. A copy of the written informed consent.
2. A record of all research tests, scores, and results.
3. Documentation of all clinical laboratory results.
4. Documentation of any concomitant medications taken by the patient.
5. A record of any and all adverse events experienced during the study.

7.5.9 Storage of data and samples:

All collected samples, including serum/plasma, blood, CSF and peripheral blood mononuclear cells (PBMC) derived from apheresis or 120cc blood sample (see 7.5.6) will be coded and stored in secured freezers on the NIH campus. All patients enrolled in this protocol will be assigned a

sequential code and all biological samples collected for this patient will be labeled with patient's code, type of the sample, volume, number of cells (if indicated) and date of freezing.

The intent is for all samples (except for those to be analyzed for idebenone and metabolite pharmacokinetics) to be analyzed in laboratories on the NIH campus. As new relevant methodologies are developed, however, there is a conceivable future interest to process samples off-site in a collaborating laboratory. Patients will be made aware of this possibility at the time of enrollment and will be asked to consent to potential off-site processing. In this event, IRB approval from NIH and from the collaborating institution will be obtained, and materials will be shipped in accordance with NIH and federal regulations.

7.6 Follow-up/termination procedures

The individual participation in the trial will end with the last trial visit at month 36, unless the trial is closed prematurely. There will be a telephone interview 1 month after completion of the trial to verify that there has been no worsening of the clinical symptoms. In case of serious adverse events ongoing at the last trial visit (month 36) **or** of SAEs newly reported during the telephone contact, the patient will be invited to undergo a full examination and assessment at the study site. Additionally, patients will be asked to report any serious adverse event that may occur after this last interview, if they perceive them as possibly related to the participation in this study. The trial will be officially terminated after all enrolled subjects complete the telephone visit (month 37) or withdraw from the trial. The trial may be terminated prematurely by the DSMB if there is a concern about safety of idebenone in PP-MS patients.

All clinical data will be prospectively acquired and entered into the NIB research database. Similarly, all neuroimaging volumetric data will be transcribed into the NIB research database. All immunological and/or biomarker data will be logged and stored in a separate research database on the NINDS server. In order to limit inter-assay variability, for those biomarkers that can be measured from cryopreserved biological samples, all time-points for individual research subjects will be run in parallel. All databases will be locked upon the last entry of data from the last patient who completes the trial.

7.6.1 Premature trial termination for futility - patient follow-up

As of this protocol amendment, the IPPoMS study 09-N-0197 (Blinded parent study of idebenone vs placebo) has completed analysis and demonstrated that idebenone, while being safe and well-tolerated, had no significant efficacy on either primary or any secondary outcome measures, in comparison to placebo. As a result, this open-label extension study will be stopped for futility. No additional patients will be enrolled onto this protocol. All participants are co-enrolled into natural history study 09-N-0032, and may continue follow-up under that study. Data and samples from this study will be transferred into protocol 09-N-0032 for continued analysis. Participants will be contacted by phone and formally informed of the study results by a written letter (uploaded to PTMS). Participants will return for a final study visit, and any remaining study drug will be collected. The final study visit will include the following procedures: clinical evaluation, MRI and safety lab work.

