11.3 Handling of missing/unobtainable data

All efforts will be made to collect a complete set of data by employing 2-4 week flexibility in scheduling and repeating inadequate quality MRI scans.

In the event that particular data points are missing for reasons other than inability to perform the test (i.e. because of disability) we will replace the missing data according to following algorithm:

- a. For data obtained every 6 months (i.e. clinical data and brain MRI data), the missing time point will be substituted by the average of 2 adjacent time-points: i.e. 6 months before and 6 months after the missing time-point. If the last time-point is missing (i.e. month 36), we will substitute the data for this time-point by the average of 2 preceding time-points.
- b. For data obtained once at treatment phase (i.e. CSF and apheresis data), the missing data cannot be replaced and the patient will be eliminated from analysis.

Handling data missing because the patient was unable to perform the test due to disability: this may happen for clinical tests such as timed 25 foot walk (25FW), 9 hole peg test (9HPT) and PASAT. These data will be calculated using the following recommendations from scoring instructions for the MSFC:

- a. 25FW: the inability to perform 25FW will be substituted by the largest Z-score in the MSFC Task force database (i.e. with the slowest time of any patient in the combined dataset used by the Task Force in its published meta-analysis). The largest Z-score in the

Task Force dataset is 13.7, therefore, for a subject who could not complete the 25FW Z_{leg} , average = -13.7 will be used.

- b. 9HPT: the inability to perform 9HPT will be coded as 777 and the following Z-score calculation formula will be applied:

$$Z_{arm, trial\#} = [(1/777 - \text{Baseline mean (1/9HPT)}) / \text{Baseline SD (1/9HPT)}]$$

- c. PASAT: In the event an individual patient cannot complete PASAT-3 due to disability, a score of 0 will be assigned.

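### Section 11 gives the early-closure final visit no stated place, so the missing-data rule understates progression on idebenone and the CSF claims no longer match who is sampled

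*Combined protocol and SAP*

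**What the plan says.** **Closure.** Section 7.6.1 ends the extension for futility and calls participants back for one last visit: "The final study visit will include the following procedures: clinical evaluation, MRI and safety lab work". In Appendix A the final-visit column ticks clinical evaluation, safety labs and brain MRI. Lumbar puncture, research blood, OCT and spine MRI are not ticked. Analysis is meant to go on: "Data and samples from this study will be transferred into protocol 09-N-0032 for continued analysis".

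**Efficacy analysis.** Section 11.2 computes an AUC for each treatment period, scaled to one year, with the stated aim of using all the data collected. It compares these AUCs in a linear mixed model. The clinical outcomes in 10.2.2 are defined over one year of idebenone. Section 11 does not mention the final visit or early closure.

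**Missing data.** Section 11.3(a) covers six-monthly data missing for any reason other than disability. For an interim gap, "the missing time point will be substituted by the average of 2 adjacent time-points"; a missing month 36 becomes the mean of the two preceding time-points. For missing CSF, 11.3(b) says that "the missing data cannot be replaced and the patient will be eliminated from analysis".

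**CSF.** Section 7.5.6 states: "Every patient will undergo a lumbar puncture at the beginning of IPPoMS-E trial (month 24) and after 1 year of therapy (month 36". According to 11.2, the original placebo arm's samples up to month 24 are all off idebenone, and the original idebenone arm has on-drug samples at months 12, 24 and 36. Primary goal 2 in 5.2 is "To extend CSF biomarker data by significantly expanding (up to 2 fold if all eligible patients proceed to IPPOMS-E", and 11.2 treats the ex-placebo patients as a confirmatory cohort.

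**Cord MRI.** Section 7.5.3 says "This scan will be performed at Mo 30 and Gd administration will be based on clinical judgment", whereas Appendix A ticks it at month 36.

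**The concern.** The schedule was amended for closure and the analysis section was not. A patient called back early has a measured value at a date that Section 11 does not recognise, and lacks one or two values that 11.3(a) says to fill in. In a disease that worsens steadily, averaging earlier values to fill a later one pulls the idebenone year towards its starting level. The main within-patient comparison sets idebenone against the patient's own baseline or placebo period, so an understated idebenone year looks like benefit. That matters in a study closed because the parent trial showed no efficacy, and whose data go on to further analysis.

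The CSF side has a separate problem. For an ex-placebo patient, month 36 is the only sample on idebenone. Closure before then leaves no pair, yet the goal and the confirmatory-cohort statement stand unchanged.

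**Working it through.** **1. The plan's own figure.** Section 11.5 expects 66 completers of the parent trial. The allocation ratio is not given here; I assume equal arms, 33 + 33. The parent trial then yields 33 idebenone pairs, and a complete ex-placebo cohort adds 33: (33 + 33)/33 = 2.0. The two-fold figure is reproduced as a ceiling.

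**2. CSF pairs after closure.** Let s be the share of ex-placebo completers who reach the month-36 lumbar puncture. Pairs = 33(1 + s), gain = 1 + s. Relative to a complete ex-placebo cohort, the standard error of its mean paired change is multiplied by 1/√s.

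| s (illustrative) | Pairs | Gain | SE factor |
|---|---|---|---|
| 1 | 66 | 2.0 | 1.0 |
| 0.75 | 57.75 | 1.75 | 1.15 |
| 0.50 | 49.5 | 1.5 | 1.41 |
| 0.25 | 41.25 | 1.25 | 2.0 |
| 0 | 33 | 1.0 | no ex-placebo pairs |

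**3. Set-up for the six-monthly outcomes.** Assume true worsening of b per 6 months, month 24 set to 0, higher meaning worse, and a trapezoid AUC with time in years. Truth: months 24, 30, 36 = 0, b, 2b, so AUC = 0.5(0 + b)/2 + 0.5(b + 2b)/2 = 0.25b + 0.75b = 1.0b.

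**4. Closed after month 30, 11.3(a) as written.** Month 36 = (0 + b)/2 = 0.5b. AUC = 0.25b + 0.5(b + 0.5b)/2 = 0.625b, which is 37.5% below 1.0b.

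**5. Closed before month 30, final visit not used.** The interim rule needs month 36 and the last-point rule needs month 30, so the pair is circular.
- Solved together: x30 = (x24 + x36)/2 and x36 = (x24 + x30)/2 give 0.75·x30 = 0.75·x24, so x30 = x36 = x24 and AUC = 0.
- With the two preceding points taken as the last two observed (months 18 and 24, values -b and 0): x36 = -0.5b, x30 = -0.25b, and AUC = -0.0625b - 0.1875b = -0.25b, an apparent improvement.

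**6. Final visit slotted in as month 30, month 36 still filled by rule.** Seen at month 27 (value 0.5b): x36 = 0.25b, AUC = 0.125b + 0.1875b = 0.3125b. Seen at month 30: 0.625b.

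**7. Final visit used, AUC only rescaled to one year.** The mean level is half the final value: 0.25b for closure at month 27, 0.5b at month 30, 0.75b at month 33, against 1.0b for a full year. Scaling per year does not correct for a shorter period.

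**8. Final visit used at its actual date in a slope.** At month 27: 0.5b over 0.25 year = 2b per year. At month 33: 1.5b over 0.75 year = 2b per year. The true slope is recovered at any closure time.

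**9. Ex-idebenone patients over three years.** Under the first reading in step 5, the values from month 0 are 0, b, 2b, 3b, 4b, 4b, 4b. The AUC per year is 8b/3 = 2.67b against 9b/3 = 3.0b, 11% too low. Only the last of three years is affected.

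**The case against.** The strongest reply is that nothing in the plan discards the final visit. Section 11.2 aims to use all collected data, and 7.5.1 accepts visits within 4 weeks of the nominal time, so a closure visit close to month 30 or month 36 could simply count as that visit. This stands: the visit lacks a stated place, not any place. It also defeats a tempting stronger reading, that early-closed patients are imputed as having no progression. That result needs the measured visit to be ignored and a circular rule to be solved simultaneously; the plan prescribes neither, and another reading gives -0.25b. The reply does not rescue the case closed after month 30 whose final visit falls outside the month-36 window. There 11.3(a) gives a definite rule and a definite error.

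Second, a reader might infer that no closed-out patient yields paired on-drug CSF. That is true only of ex-placebo patients. Ex-idebenone patients have months 12 and 24 on drug and lose only the third such sample. The month-24 sample also keeps a use in the ex-placebo arm, as its third off-therapy point.

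Third, one might argue that the closure visit should have included the lumbar puncture and cord scan. The documents do not support calling their absence an error. Of the lumbar puncture, 7.5.6 says "This procedure is performed solely for research purposes", and omitting it at a futility closure may well be deliberate. The cord omission rests on Appendix A alone, because 7.6.1 names no region, and under the 7.5.3 timing a patient closed after month 30 would already have been scanned.

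Fourth, the two-fold figure is explicitly conditional and theoretical. The confirmatory test also covers only biomarkers that changed significantly in the parent trial, which reported no effect on its primary or any secondary outcome. If CSF markers were secondary outcomes there (the list is not shown), little may remain to confirm. That lowers the stakes, but the text still describes a cohort that closure has cut short.

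**Conclusion.** The point holds in limited form. Section 11 does not say how the closure visit is analysed, and 11.3(a), as written, understates progression on idebenone for patients who lose month 36 to closure: 0.625b against 1.0b for closure after month 30. Before month 30 the rule is undefined; if the final visit is not used, the readings give 0 or -0.25b. All of these errors favour idebenone.

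These sizes assume linear worsening and describe the AUC above the month-24 level for one patient. For ex-idebenone patients the error is diluted by two earlier years on drug. The numbers closed before months 30 and 36 are not given, so neither the trial-level bias nor the loss of CSF pairs can be computed; the shares in the table are illustrations. Ex-placebo patients closed before month 36 contribute no CSF pair, and 5.2 and 11.2 should say so.

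**What to change.** 1. In 11.2 and 11.3, state that 11.3(a) does not apply to visits prevented by trial closure. Analyse the measured values, including the final visit, at their actual dates and time on drug, using a slope or a mixed model in time. Do not rely on per-year scaling of the AUC, which leaves the bias in step 7.
2. Restate goal 2 in 5.2 and the two-fold and confirmatory-cohort statements in 11.2 for the ex-placebo patients who have an on-drug month-36 sample. Report that number and the gain it implies, 1 + s under equal arms.
3. Reconcile the cord MRI timing between 7.5.3 and Appendix A, so that it is clear which closed-out patients should have an extension cord scan.

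These are changes of wording and analysis code. They need no new procedure, visit or sample. Some power for the CSF comparison is lost, but closure has already caused that loss; the restatement only reports it.
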